## LIST OF ABBREVIATIONS & DEFINITIONS

CYP2C19	cytochrome P450 2C19
GCP	Good Clinical Practice
HUP	Hospital of the University of Pennsylvania
HrQOL	health related quality of life
ICER	Incremental cost effectiveness ratio
ICH	International Conference on Harmonization
LOF	loss of function
PCI	percutaneous coronary intervention
PGx	pharmacogenetics
PPMC	Penn Presbyterian Medical Center
PHI	Protected health information
QALYs	Quality adjust life years
TIA	Transient ischemic attack

## SYNOPSIS

Title	Assessment of prospective CYP2C19 genotype guided Dosing of Anti-Platelet Therapy in Percutaneous Coronary Intervention ( ADAPT )
Objectives	
 
• To determine the effect of CYP2C19 genotyping on the prescribing of antiplatelet therapies following PCI
 
• To identify factors linked with successful implementation of clinical pharmacogenetic (PGx) testing in a large academic medical center.
 
• To determine the rates of clinical outcomes.
 
• To conduct a prospective pilot study to determine means and variances for cost, quality adjusted life years (QALYs), and the correlation of cost and effect.
 

Study Design	
The study utilizes a novel genotyping device, SpartanRx™ (Spartan Bioscience, Ottawa, Canada) that provides identification of a patient's CYP2C19 *2, *3, and *17 genotypes determined from genomic DNA from a buccal swab sample with 1 hour turnaround time.
 
PCI Patient Study
 
This is a randomized, prospective, pragmatic open label study. Patients undergoing percutaneous intervention (PCI) with stent implantation, who require anti-platelet therapy, will be randomized either to: Arm 1) genotype guided dosing of antiplatelet therapy or Arm 2) usual care.
 
In Arm 1, a buccal swab will be obtained from subjects immediately following PCI/stent, to determine CYP2C19 genotype with the SpartanRx system. Subject with slow metabolizer status [1 or 2 loss-of-function (LOF) mutations (*2 or *3) in CYP2C19] will be recommended to initiate therapy with prasugrel or ticagrelor in place of clopidogrel. Subjects with normal metabolizer status (homozygous for the *1 allele in CYP2C19) will be recommended to initiate therapy with clopidogrel. Antiplatelet choice is ultimately decided by physician judgment incorporating all clinical factors.
 
In Arm 2, choice of antiplatelet therapy will be decided by treating physician as per usual care. DNA will be collected via a saliva sample to assess CYP2C19 genotype at the conclusion of the study.
 
Subjects in both groups will complete a baseline health related quality of life questionnaire (HrQoL) and additional clinical data pertaining to cardiac history will be collected from medical records. Subjects will be contacted every three months for medical services utilization, clinical information, and HrQoL assessments for a total of one year. Medical records will be reviewed for clinical outcomes until May 31, 2017.

Study Duration	3 years
Study Centers	Hospital of the University of Pennsylvania (HUP) Penn Presbyterian Medical Center (PPMC)
Primary Objective	To determine the effect of CYP2C19 genotyping on the prescribing of antiplatelet therapies following PCI.
Secondary and Tertiary Objectives	
 
1. To determine physician adherence to genotype guided recommendations.
 
2. To determine clinical outcomes (myocardial infarction, stroke, stent thrombosis, revascularization, death and bleeding)
 
3. To determine means and variances needed for economic evaluation
 

	
including cost, QALYs, and the correlation between cost and effect.
 
 
To estimate the incremental cost per quality-adjusted life year (QALY) ratio
 
Assess patient and prescriber attitudes towards PGx testing.
 

Number of subjects	500-600
Inclusion criteria	
 
Male and female subjects, <math>\geq 18</math> to <math>\leq 80</math> years at time of study
 
Status post PCI with stent implantation requiring antiplatelet therapy
 
Willingness to comply with all study-related procedures
 

Exclusion criteria	
 
Pending imminent surgery placing patients at increased risk for bleeding with prasugrel or ticagrelor.
 
History of intracranial hemorrhage, transient ischemic attack (TIA), stroke
 
Active bleeding
 
Need for long-term anticoagulation (i.e. warfarin, dabigatran, rivaroxaban, apixaban, edoxaban, or lovenox).
 
Current or prior (within the past four weeks) treatment with voraxapar (Zontivity).
 
Severe renal or hepatic impairment
 
Treating physician does not want subject to participate
 

Statistical methodology	
For the primary outcome the number (proportion) of participants receiving prasugrel/ticagrelor in each randomized arm will be determined. The adherence rate will be determined as the number of participants in genotyped arm with LOF variants that received prasugrel or ticagrelor + the number of participants without these variants that received clopidogrel divided by the total number. For categorical variables, frequencies and percentages will be presented. For continuous variables, the number of subjects, mean, standard deviation, minimum, 25th percentile, median, 75th percentile and maximum will be presented. Reported differences will include standard errors and 95% CI. Analyses will be based on the modified intention to treat.

## 1.0 ETHICS

The study will be conducted in accordance with the site's clinical research standards that meet regulations relating to Good Clinical Practice (GCP). These standards adhere to the following guidelines:

- Good Clinical Practice: ICH Consolidated Guideline (International Conference on Harmonization of Technical Requirements for the Registration of Pharmaceuticals for Human Use, May 1997).
- United States (US) Code of Federal Regulations (21 CFR) dealing with human subject protection and conduct of investigational clinical studies (21 CFR parts 50, 54, 56, 312, and 314).
- Declaration of Helsinki, concerning medical research in humans ("Recommendations Guiding Physicians in Biomedical Research Involving Human Subjects," Helsinki 1964, amend Tokyo 1975, Venice 1983, Hong Kong 1989 and revised version of Somerset West, Republic of South Africa, October, 1996).

## 2.0 INTRODUCTION

Clopidogrel is a thienopyridine antiplatelet agent, which inhibits the purinergic P2Y12 receptor on platelets and prevents their aggregation. It is commonly used in patients with acute coronary syndromes (ACS) undergoing percutaneous coronary intervention (PCI). *CYP2C19* is one of the principal enzymes involved in the bioactivation of clopidogrel from the pro-drug to its active metabolite. The most common loss of function (LOF) allele is \*2 (c.681G>A; rs4244285), with frequencies of ~15% in Caucasians and Africans and 29-35% in Asians. A large meta-analysis performed by Mega and colleagues demonstrated that *CYP2C19*\*2 carriers treated with clopidogrel have a higher risk for major adverse cardiac events compared to noncarriers (hazard ratio (HR) of 1.55, 95%CI 1.11-2.17 for heterozygotes; HR 1.76, 95% CI 1.24-2.50) and higher risk of stent thrombosis (HR 2.67, 95% CI 1.69-4.22 for heterozygotes; HR 3.97, 95% CI 1.75-9.02 for homozygotes). Therefore, clopidogrel is less effective in patients who are *CYP2C19* poor metabolizers and alternative therapy is recommended.

A newer-generation thienopyridine, prasugrel, was found to be associated with a reduction in major adverse cardiac events (death, myocardial infarction, stroke) compared to clopidogrel, but with an increased risk of fatal and major bleeding events.

While a body of observational literature and clinical guidelines suggest prescribing alternative antiplatelet therapy in carriers of *CYP2C19* LOF alleles, it is unknown whether physicians will follow genotype guided recommendations when pharmacogenetic (PGx) results are presented to them in a real world setting. To provide evidence regarding the implementation and effectiveness of PGx testing following PCI, we will examine the differences in prescribing of antiplatelet drugs when presented with genotype data. We will also evaluate physician's adherence to the genotype guided antiplatelet recommendations.

Now that clopidogrel is available in generic form, pharmacogenetic (PGx) screening could allow for individualized anti-platelet therapy in which patients with functional *CYP2C19* alleles could be prescribed clopidogrel, and the more expensive agent would be reserved for patients with poor metabolizer status. A cost-effectiveness analysis of *CYP2C19* screening for selection of antiplatelet therapy found that genotype-guided therapy would lead to more cost-effective care rather than uniform usage of either clopidogrel or prasugrel. Genotyping produced 450 fewer cardiovascular events compared with treating all patients with clopidogrel. The number needed to genotype (NNG) was 23, i.e. one excess cardiovascular event was avoided for every 23 patients genotyped when compared to a clopidogrel-for-all strategy. The NNG was 30 when comparing genotype guided therapy to prasugrel-

for- all. Cost-savings were not evident when genotype-guided therapy was compared to generic clopidogrel for all patients. The analysis did not examine quality measures that are important in assessing patient outcomes.

A more recent economic evaluation determined that genotyping and prescribing ticagrelor to LOF allele carriers was the most effective strategy when compared against routine clopidogrel or prasugrel use as well as genotyping and prescribing prasugrel to LOF carriers. However, these results were based on decision model of a hypothetical cohort of patients with ACS who underwent PCI and several assumptions were made regarding outcomes, cost and quality of life. True costs associated with genotype guided antiplatelet therapy are unknown. Future prospective studies evaluating the cost effectiveness of a genotype guided approach are needed. We are proposing a pilot study which will provide information necessary for planning a prospective study that will directly estimate events averted, costs, QALYs and cost per QALY ratios. Information to be obtained in this pilot includes estimates of costs and their variance, preference scores (for calculating QALYs) and their variance, the correlation of cost and effects (required for sample size estimation for cost-effectiveness ratios), event rates, and implementation metrics (to estimate likely penetration of testing in the trial). The results from this study will provide more accurate estimates of the means and variances of cost and QALYs required to plan future trials. We will also examine the cost-effectiveness of genotyping for *CYP2C19* in daily clinical practice.

### **3.0 OBJECTIVES**

- To determine the effect of *CYP2C19* genotyping on the prescribing patterns of antiplatelet therapies following cardiac catheterization.
- To determine the rates of clinical outcomes.
- To identify factors linked with successful implementation of clinical pharmacogenetic (PGx) testing in a large academic medical center.
- To conduct a prospective pilot study to determine means and variances for cost, quality-adjust life years (QALYs), and the correlation of cost and effect.
- Assess patient and prescriber attitudes towards PGx testing.

### **4.0 STUDY DESIGN**

[figure not shown]
This is a randomized, prospective, pragmatic open label pilot study (Figure 1). Patients undergoing PCI with stent implantation, who require anti-platelet therapy, will be randomized to: Arm 1) genotype guided dosing of antiplatelet therapy or Arm 2) usual care. Randomization will be stratified by the occurrence of acute coronary syndrome (ACS).

In Arm 1, a buccal swab will be obtained from subjects immediately following PCI/stent, to determine *CYP2C19* genotype with the SpartanRx system. This arm provides pharmacogenetic information to help guide decision making: initiation of therapy with prasugrel or ticagrelor will be recommended for participants found to be slow metabolizers [1 or 2 loss-of-function (LOF) mutations (\*2 or \*3) in *CYP2C19*]; initiation of therapy with clopidogrel will be recommended for participants found to be normal metabolizers (*CYP2C19* \*1/\*1). See Table 1 and Appendix A. Antiplatelet choice will ultimately be decided by the treating physician taking into account all clinical factors.

In Arm 2, the choice of antiplatelet therapy will be decided by the treating physician as per usual care. DNA will be collected by –saliva sample and *CYP2C19* genotype will be determined at the completion of the study.

Subjects in both groups will complete baseline health related quality of life questionnaire (HrQoL). Subjects will be contacted every three months for clinical information, medical service utilization and HrQoL assessments. No specific recommendations will be made regarding use of vorapaxar, a recently approved anti-platelet agent for which guideline-based recommendations regarding genotyping are not available.

**Figure 1. Clinical Trial Study Design and Endpoints**

#### 4.1 Primary endpoint

- Number of participants receiving prasugrel/ticagrelor in each arm.

#### 4.2 Secondary endpoints

1. Implementation
  - a. Adherence to suggested treatment recommendations based on genotype
  - b. Reasons for non-adherence to recommendations Medical service utilization
2. Clinical Outcomes
  - a. Major adverse cardiac event (CV related death, MI, stroke, urgent need for revascularization, stent thrombosis, all deaths).
  - b. Bleeding complications (defined by the Bleeding Academic Research Consortium).
  - c. Clinical outcomes will be ascertained by medical records until May 31, 2017.
3. Economic- Incremental cost effectiveness ratio per quality adjusted life-year (ICER/QALYs).
  - a. Medical services utilization
  - b. Cost of services
  - c. Preference score (SF-12 questionnaire) performed at baseline and every 3 months for one year for determination of QALYs.

#### 4.3 Tertiary Endpoints

- a. Additional implementation metrics
  - a. Number of genotype results returned
  - b. Average genotype test completion time
  - c. Genotype assay failure rate (inconclusive test result)
  - d. Number/reason for screening failure
  - e. Time from test order to result in medical record
- b. Patient attitudes towards PGx testing as determined by questionnaire will be completed at the 3 month phone follow-up.
- c. Prescriber attitudes towards PGx testing as determined by questionnaire that will be administered at the start and end of the study.

**Table 1. Treatment recommendations for antiplatelet therapy based on CYP2C19 genotype**

Genotype	Phenotype	Description	Treatment a
CYP2C19 *1/*1	Extensive metabolizer (normal)	Two inferred normal alleles	Clopidogrel 75 mg per day
CYP2C19 *1/*17	Ultra-rapid metabolizer	One inferred normal allele One increased function allele	
CYP2C19 *17/*17		Two gain of function alleles	
CYP2C19 *1/*2	Intermediate metabolizer	One inferred normal allele One loss of function allele	Prasugrel (Effient) 10 mg per day b Or Ticagrelor (Brilinta) 90 mg twice daily c
CYP2C19 *1/*3		One inferred normal allele One loss of function allele	
CYP2C19 *2/*17		One loss of function allele One gain of function allele	
CYP2C19 *3/*17		One loss of function allele One gain of function allele	
CYP2C19 *2/*2	Poor metabolizer	Two loss of function alleles	Prasugrel (Effient) 10 mg per day b Or Ticagrelor (Brilinta) 90 mg twice daily c
CYP2C19 *3/*3		Two loss of function alleles	
CYP2C19 *2/*3		Two loss of function alleles	

a Please consider all clinical contraindications before prescribing alternative antiplatelet agent.

Prasugrel and ticagrelor are recommended only when not clinically contraindicated.

b Consider prasugrel 5 mg per day for patients <60 kg.

Individual risks/benefits of prasugrel must be carefully considered in patients over age 75.

Do not use prasugrel in patients with active bleeding or a history of transient ischemic attack or stroke.

Do not start prasugrel in patients likely to undergo **urgent** coronary bypass graft surgery (CABG).

c Do not use ticagrelor in patients with active bleeding or a history of transient ischemic attack or stroke.

Do not start ticagrelor in patients likely to undergo **urgent** coronary bypass graft surgery (CABG).

Do not use maintenance aspirin doses above 100 mg in combination with ticagrelor.

## 5.0 STUDY POPULATION

All patients undergoing PCI with stent implantation at HUP or PPMC who will require clopidogrel, prasugrel or ticagrelor treatment will be considered for this protocol.

### 5.1 Inclusion Criteria

1. Male and female subjects,  $\geq 18$  to  $\leq 80$  years at time of study
2. Status post PCI with stent implantation requiring antiplatelet therapy
3. Willingness to comply with all study-related procedures

### 5.2 Exclusion criteria:

1. Pending imminent surgery placing patients at increased risk for bleeding with prasugrel or ticagrelor.
2. History of intracranial hemorrhage, TIA, and stroke
3. Active bleeding

4. Need for long-term anticoagulation (i.e. warfarin, dabigatran, rivaroxaban, apixaban, edoxaban, or lovenox).
5. Current or prior (within the past four weeks) treatment with voraxapar (Zontivity).
6. Severe renal or hepatic impairment
7. Treating physician does not want subject to participate

## **6.0 STUDY PROCEDURES**

### **6.1 Informed Consent**

Subjects will be approached for enrollment 2 hours following their PCI/stent implantation in the holding area or their inpatient hospital bed by the research coordinator.

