## Appendix A. Treatment recommendations handout for interventional cardiologist

Table 1. Treatment recommendations for antiplatelet therapy based on CYP2C19 genotype

Genotype	Phenotype	Description	Treatment a
CYP2C19 *1/*1	Extensive metabolizer (normal)	Two inferred normal alleles	Clopidogrel (Plavix) 75 mg per day
CYP2C19 *1/*17		One inferred normal allele One increased function allele	
CYP2C19 *17/*17		Two gain of function alleles	
CYP2C19 *1/*2	Intermediate metabolizer	One inferred normal allele One loss of function allele	Prasugrel (Effient) 10 mg per day b  Or  Ticagrelor (Brilinta) 90 mg twice daily c
CYP2C19 *1/*3		One inferred normal allele One loss of function allele	
CYP2C19 *2/*17		One loss of function allele One gain of function allele	
CYP2C19 *3/*17		One loss of function allele One gain of function allele	
CYP2C19 *2/*2	Poor metabolizer	Two loss of function alleles	Prasugrel (Effient) 10 mg per day b  Or  Ticagrelor (Brilinta) 90 mg twice daily c
CYP2C19 *3/*3		Two loss of function alleles	
CYP2C19 *2/*3		Two loss of function alleles	

Table 2. Switching recommendations based on CYP2C19 genotype

Genotype CYP2C19	Initial loading dose	Reload	Maintenance a
*1/*2, *1/*3, *2/*2, *3/*3, *2/*17, *3/*17	Clopidogrel 600 mg	Prasugrel 60 mg	Prasugrel 10 mg b
		Ticagrelor 180 mg	Ticagrelor 90 mg c
*1/*1, *1/*17, *17/*17	Prasugrel 60 mg	Not needed	Clopidogrel 75 mg
	Ticagrelor 180mg	Clopidogrel 300 mg	Clopidogrel 75mg

a Please consider all clinical contraindications before prescribing alternative antiplatelet agent. Prasugrel and ticagrelor are recommended only when not clinically contraindicated. See table 3 below

Table 3. Clinical Contraindications to Prasugrel or Ticagrelor

Prasugrel b	Ticagrelor c

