### Section 3: Study Methods

Section/Item	Index	Description
Trial Design	9	This was a prospective, pragmatic, randomized, controlled clinical pharmacogenetic implementation trial. Patients undergoing PCI with stent implantation requiring anti-platelet therapy were randomized 1:1 to either rapid genotyping of CYP2C19 with reporting of results to the interventional cardiologist or no genotyping (usual care).
Randomization	10	We used Stata's V13.1 (College Lake, TX) random number generator to draw random numbers that were used to randomize participants to the genotyping and usual care groups. Randomization was stratified by hospital site and by the presence or absence of ACS. Acute coronary syndrome was defined as unstable angina, non-ST elevation myocardial infarction, or ST-elevation myocardial infarction. The designation of ACS vs. stable angina was made by the treating interventional cardiologist. Within each of the four groups, randomization was balanced so that after every 10 patients, 5 were randomized to the genotyped group and 5 to usual care.
Sample size	11	The sample size calculation was based on two factors: 1) the rate of pre-study prasugrel/ticagrelor use (20%) and 2) anticipated increase in prasugrel/ticagrelor prescribing based on the frequency CYP2C19 LOF variants (~30-35%). We estimated a 15% difference in the use of prasugrel/ticagrelor in the two groups (35% in the genotyped group and 20% in the control group). A sample size of 138 per group (a total of 276) would provide 80% power at an alpha level of 0.05 to detect this difference. We increased our sample size to ~250 per group to allow for subgroup comparisons (e.g. ACS vs. stable coronary disease).
Framework	12	Genotyping will increase the prescribing of prasugrel or ticagrelor from the baseline rate of 20%.
Statistical interim analyses and stopping guidance	13	No interim analyses planned.
Timing of final analysis	14	Participants were followed until May 31, 2017 for prospective clinical endpoints assessment with the intention of a 12 month follow-up time for each participant. All analyses were performed collectively after May 31, 2017.

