## Section 5: Trial Population

Section/Item	Index	Description
Screening data	21	The number of PCIs performed, participants screened, and reasons for screening failure were collected by each study site. These data were reviewed by study staff to monitor recruitment and enrollment progress throughout the study.
Eligibility	22	
Inclusion Criteria
 
 
1. Male and female subjects, <math>\geq 18</math> to <math>\leq 80</math> years at time of study
 
2. Status post PCI with stent implantation requiring antiplatelet therapy
 
3. Willingness to comply with all study-related procedures
 
 
Exclusion criteria:
 
 
1. Pending imminent surgery placing patients at increased risk for bleeding with prasugrel or ticagrelor.
 
2. History of intracranial hemorrhage, TIA, and stroke
 
3. Active bleeding
 
4. Need for long-term anticoagulation (i.e. warfarin, dabigatran, rivaroxaban, apixaban, edoxaban, or lovenox).
 
5. Current or prior (within the past four weeks) treatment with voraxapar (Zontivity).
 
6. Severe renal or hepatic impairment
 
7. Treating physician does not want subject to participate
 

Recruitment	23	The number of participants assessed for eligibility along with reasons for non-enrollment will be reported as available.
Withdrawal/ follow-up	24a	The numbers of withdrawal from follow-up clinical assessments were reported as the intervention is a one-time event.
	24b	The number and time post randomization of voluntary withdrawals by participants or lost to follow-up were reported.
	24c	Reasons for voluntary withdrawal or lost to follow-up were reported if available.
Baseline patient characteristics	25a	Sex, race, age, hospital site, presence of acute coronary syndrome (ACS), insurance type, work status, tobacco use, past medical history, medications prior to admission.
	25b	For categorical variables, frequencies and percentages were reported. For continuous variables, the number of subjects, mean and standard deviation were reported by randomization group.

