## Section 6: Analysis

Section/Item	Index	Description
Outcome definitions	26a	
Primary outcome: The number and proportion of participants receiving prasugrel/ticagrelor at discharge from index PCI in each randomized. Timing <7 days
 
Secondary Outcomes:
 
 
1. Adherence to the CPIC guideline suggested antiplatelet therapy recommendations based on genotype (intervention group only). Timing <7 days.
 
2. Major adverse cardiac events (MACE) defined as cardiovascular death, myocardial infarction, stroke, urgent need for revascularization, and stent thrombosis (Academic Research Consortium “definite” stent thrombosis). Timing at last follow-up.
 
3. Major bleeding events as defined by the Bleeding Academic Research Consortium (BARC) type 3 or 5. Timing at last follow-up.
 
4. Non-cardiac mortality. Timing at last follow-up.
 
5. Implementation Metrics. Timing < 7days 
 
a. Genotype test turnaround time (Time result reported to physician – time of buccal swab).
 
b. Number of inconclusive results.
 
 
 

	26b	n/a
	26c	Time to MACE or major bleed

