Analysis methods	27a	
Primary outcome: Discharge antiplatelet therapy choice by genotyped and usual care group was compared using the chi-square or Fisher's exact test. The probability of receipt of antiplatelet agents was determined by logistic regression.
 
Secondary outcomes:
 
 
1. The adherence rate to the genotype guided recommendations for the genotyped group was determined by reporting the number of participants with LOF variants that received prasugrel or ticagrelor + the number of participants without these variants that received clopidogrel divided by the total number in the genotyped arm.
 
2. Clinical outcomes. Frequencies of CV related death, MI, stroke urgent, need for revascularization and stent thrombosis was reported as well frequencies of bleeding complications and compared using chi-square test or Fisher's exact test when appropriate. The time to first major cardiac event as a composite endpoint (CV related death, MI, stroke urgent need for revascularization and stent thrombosis) was determined. The incidence of first MACE and first major bleeding events between the groups was compared by use of Kaplan-Meier estimators and statistical tests evaluated based on log-rank tests.
 
3. Implementation. The turnaround time for test result in the
 

		genotyped group was presented as mean ± standard deviation (hours).
27b	n/a	
27c	n/a	
27d	n/a	
27e	n/a	
27f		To evaluate whether genotyping influenced MACE outcomes in participants with ACS, an interaction term between ACS and group assignment was tested in a Cox proportional hazard model.
Missing data	28	For time to MACE analysis, participants were censored at the date of event or time of known last follow-up.

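### The P2Y12 agent already given before randomisation is missing from the baseline list and the analysis: a cheap gain in precision, and in showing two-way switching, is left unused

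*Protocol*

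**What the plan says.** On timing, the protocol makes two statements. Section 6.1: "Subjects will be approached for enrollment 2 hours following their PCI/stent implantation in the holding area or their inpatient hospital bed". Section 4.0, for Arm 1: "a buccal swab will be obtained from subjects immediately following PCI/stent"; the synopsis agrees with Section 4.0. The synopsis gives the genotyping device a turnaround of 1 hour.

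On what has been given by then, Section 4.0 speaks of recommending that a drug be initiated. The handout in Appendix A contains "Table 2. Switching recommendations based on CYP2C19 genotype", whose columns run from an initial loading dose, through a reload, to maintenance.

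On data and analysis:
- The SAP baseline list (item 25a) ends with "tobacco use, past medical history, medications prior to admission". It has no entry for an agent given around the procedure.
- On allocation, SAP item 10 says "Randomization was stratified by hospital site and by the presence or absence of ACS". Protocol 4.0 names ACS only. Neither uses the loaded agent.
- The primary outcome (SAP item 26a) is "The number and proportion of participants receiving prasugrel/ticagrelor at discharge from index PCI".
- The primary analysis (SAP item 27a) is "Discharge antiplatelet therapy choice by genotyped and usual care group was compared using the chi-square or Fisher's exact test", followed by "The probability of receipt of antiplatelet agents was determined by logistic regression". No covariates are named.
- Adherence, and the reasons for not following the recommendation, are assessed in the genotyped arm only (SAP item 19a).

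**The concern.** If a first agent has been loaded before randomisation, the genotype result can act only by keeping or changing it. That agent is then probably a strong predictor of the discharge agent, and it is known before allocation. An analysis that ignores it gives up precision.

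The second loss concerns description. The recommendation works in both directions: loss-of-function (LOF) carriers towards prasugrel or ticagrelor, the others towards clopidogrel. The primary endpoint records only the net share at discharge, so changes in opposite directions cancel. The introduction asks whether physicians will act on genotype results, and the net share answers that only in part.

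**Working it through.** **1. The plan's own figure.** Inputs from Protocol 7.5 and SAP item 11: 35% against 20%, 80% power, alpha 0.05 (taken as two-sided). With mean rate 0.275:

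n = [1.960 × √(2 × 0.275 × 0.725) + 0.842 × √(0.35 × 0.65 + 0.20 × 0.80)]² / 0.15² = [1.238 + 0.524]² / 0.0225 ≈ 138 per group.

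This reproduces the stated 138. At 250 per group the same method gives power 0.966.

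**2. Validity of the crude test.** In 20,000 simulated trials per scenario with strong persistence of the loaded agent, the type I error of the crude chi-square was 0.049 (138 per arm) and 0.051 (250 per arm). At 250 per arm the mean crude difference was 0.150, 0.120 and 0.090 where the true values were the same. There is no bias.

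**3. Precision, base case.** The loading and persistence rates here and in step 4 are assumptions. Suppose 20% are loaded with prasugrel/ticagrelor. The share of each loading group discharged on prasugrel/ticagrelor is:
- usual care: 85% and 3.75%, so 0.2 × 0.85 + 0.8 × 0.0375 = 0.20;
- genotyped: 60% and 28.75%, so 0.2 × 0.60 + 0.8 × 0.2875 = 0.35.

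Variance of the risk difference, multiplied by n per arm:
- Crude: 0.35 × 0.65 + 0.20 × 0.80 = 0.3875.
- Standardised, within strata: 0.2 × (0.85 × 0.15 + 0.60 × 0.40) + 0.8 × (0.0375 × 0.9625 + 0.2875 × 0.7125) = 0.2663.
- Standardised, for unequal stratum effects (−0.25 and +0.25 around a mean of 0.15): ½ × [0.2 × 0.40² + 0.8 × 0.10²] = 0.02.
- Total 0.2862; ratio 0.2862 / 0.3875 = 0.74, a 26% cut in variance.

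At 250 per arm the SE falls from √(0.3875/250) = 3.9 points to √(0.2862/250) = 3.4 points. Power goes from Φ(0.15/0.0394 − 1.96) = 0.968 to Φ(0.15/0.0338 − 1.96) = 0.993. (The 0.968 uses the unpooled SE; the 0.966 in step 1 uses the pooled one.)

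**4. Precision over a range.** Assumed: 20% loaded with prasugrel/ticagrelor and a usual-care discharge rate of 20%. Weak persistence means that 70% of those loaded with prasugrel/ticagrelor and 92.5% of those loaded with clopidogrel stay on it; strong means 90% and 97.5%. Where the genotype is not followed, prescribing is as in usual care. Results at 250 per arm:

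| LOF share; genotype followed in | Difference | SE ratio | Power, crude | Power, adjusted |
|---|---|---|---|---|
| 35%; 100% | 15 points | 0.92–0.96 | 0.968 | 0.978–0.986 |
| 35%; 80% | 12 points | 0.88–0.94 | 0.870 | 0.908–0.941 |
| 35%; 60% | 9 points | 0.82–0.91 | 0.653 | 0.732–0.819 |
| 30%; 100% | 10 points | 0.91–0.96 | 0.739 | 0.775–0.812 |

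The largest gain is an SE ratio of 0.81 (LOF 30%, followed in 60%, strong persistence). The SE cut is therefore about 4 to 19%. In variance, 1 − 0.96² = 8% to 1 − 0.82² = 33% at LOF 35%, and 1 − 0.81² = 34% at the extreme. At the planned 35% against 20%, power rises by 1 to 2 points in the table and by 2.5 points in the base case.

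**5. What the net share leaves out.** Take LOF 35%, a loading share of 20%, genotype independent of loaded agent, and every recommendation followed. Then 0.80 × 0.35 = 28% switch up and 0.20 × 0.65 = 13% switch down. The net is 15 points, the planned difference, although 28 + 13 = 41% of the genotyped arm changed agent. Conversely, physicians who ignored every result and kept the loaded agent would still score 0.65 × 0.80 + 0.35 × 0.20 = 59% on the adherence rate.

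**The case against.** The strongest reply is that nothing is wrong with the primary analysis. The loaded agent is fixed before allocation, so the arms are balanced on it in expectation. The 138 already carries the full binomial variance at 20% and 35%. A reader might infer that the omission adds noise beyond what was planned for, or hides the effect of genotyping. The documents support neither: this is a gain forgone, and power at the planned rates is ample.

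It can also be said that reluctance to change a loaded agent belongs to the pragmatic effect being estimated. That stands. Such reluctance lowers the true difference, and adjustment does not restore it.

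Three further readings are tempting and not supported:
- That randomisation falls at least 2 hours after PCI. Section 6.1 gives 2 hours for the approach to enrol, while Section 4.0 and the synopsis place the swab directly after the procedure.
- That the result usually reaches a physician who has already chosen. No loading frequency is given; Appendix A shows only that the case was foreseen.
- That the loaded agent is excluded from the model. The logistic regression names no covariates, so the agent is unspecified. Protocol 6.3 collects baseline clinical data from medical records without listing the items, so the field may exist even though SAP item 25a omits it.

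The adherence endpoint and the reasons for non-adherence cover part of the descriptive gap. They do not distinguish a changed prescription from an unchanged one that happens to match the genotype, and they have no counterpart in usual care.

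**Conclusion.** This is a cheap improvement and not an error in the primary test. The crude arm comparison is unbiased, holds its type I error, and has power 0.966 at 250 per arm for 35% against 20%.

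The forgone precision matters little at the planned rates and more if the genotype is followed less often. All of these sizes rest on assumed loading and persistence rates. They also compare adjustment with no adjustment at all; if ACS and site predict the choice of agent, the gain beyond adjusting for those two would be smaller.

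The clearer benefit is descriptive. A table of pre-randomisation agent by discharge agent shows both directions of switching in both arms, which neither the discharge share nor the adherence rate can do.

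**What to change.** 1. Add to SAP item 25a the P2Y12 agent given before randomisation, including the procedural load, with a category for none recorded. Abstract it from the medical record already used for baseline data.
2. Keep the discharge endpoint and the chi-square or Fisher test as primary. In item 27a add a supporting risk difference standardised over the pre-randomisation agent, ACS and site, or a Mantel-Haenszel analysis stratified by them. If a logistic model is used, let the arm effect differ by pre-randomisation agent and standardise the fitted probabilities. The arm coefficient alone is a conditional odds ratio and does not deliver the precision gain shown above.
3. Tabulate pre-randomisation agent by discharge agent in each arm, as supporting description and not as a replacement for the primary effect.
4. Reconcile the swab timing in Protocol 4.0 and the synopsis with the approach time in 6.1.

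The cost is one abstracted field, a category for missing information, and a few lines of SAP text. The SAP is written in the past tense, so anything added after data review should be labelled post hoc.
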